5.11 Discontinuation of Study Treatment

Treatment will continue at the prescribed dose level until the occurrence of any of the following events.

- Disease progression
- Adverse event(s) that, in the judgment of the Investigator, may cause severe or permanent harm or which rule out continuation of the treatment regimen.
- Intolerance of lenalidomide or everolimus for any reason.
- Major violation of the study protocol.
- Withdrawal of consent
- Lost to follow up
- Death
 - Suspected pregnancy or positive pregnancy

5.12 Follow-Up

Subjects who discontinue treatment for any reason, will not be followed if they have no residual toxicity (\geq grade 3) attributable to the study drugs at the time of the final safety assessment planned for approximately 30 days post the last dose of protocol therapy. If otherwise indicated by persistent grade \geq 3 toxicity, patients will be followed by telephone contact every 30 days. In addition off study evaluations per the Schedule of Assessments, Section 2 will be done.

6 Adverse events

6.1 Serious Adverse Event (SAE) Definition

A serious adverse event is one that at any dose (including overdose):

- Results in death
- Is life-threatening¹

Requires inpatient hospitalization or prolongation of existing hospitalization

- Results in persistent or significant disability or incapacity²
- Is a congenital anomaly or birth defect
- Is an important medical event³
- Pregnancy

¹“Life-threatening” means that the subject was at immediate risk of death at the time of the serious adverse event; it does not refer to a serious adverse event that hypothetically might have caused death if it were more severe.

²“Persistent or significant disability or incapacity” means that there is a substantial disruption of a person’s ability to carry out normal life functions.

³Medical and scientific judgment should be exercised in deciding whether expedited reporting is appropriate in situations where none of the outcomes listed above occurred. Important medical events that may not be immediately life-threatening or result in death or hospitalization but may jeopardize the patient or may require intervention to prevent one of the other outcomes listed in the definition above should also usually be considered serious. Examples of such events include allergic bronchospasm requiring intensive treatment in an emergency room or at home, blood dyscrasias or convulsions that do not result in inpatient hospitalization, or the development of drug dependency or drug abuse. A new diagnosis of cancer during the course of a treatment should be considered as medically important.

6.2 Adverse Drug Reaction Reporting - Lenalidomide

Toxicity will be scored using CTCAE Version 4.0 for toxicity and adverse event reporting. A copy of the CTCAE Version 4.0 can be downloaded from the CTEP homepage ([HTTP://CTEP.INFO.NIH.GOV](http://CTEP.INFO.NIH.GOV)

OR

[HTTP://CTEP.CANCER.GOV/PROTOCOLDEVELOPMENT/ELECTRONIC_APPLICATIONS/DOCS/CTCAEV4.PDF](http://CTEP.CANCER.GOV/PROTOCOLDEVELOPMENT/ELECTRONIC_APPLICATIONS/DOCS/CTCAEV4.PDF)). All appropriate treatment areas should have access to a copy of the CTCAE Version 4.0. All adverse clinical experiences, whether observed by the investigator or reported by the patient, must be recorded, with details about the duration and intensity of each episode, the action taken with respect to the test drug, and the patient’s outcome. The investigator must evaluate each adverse experience for its relationship to the test drug and for its seriousness.

The investigator must appraise all abnormal laboratory results for their clinical significance. If any abnormal laboratory result is considered clinically significant, the investigator must provide details about the action taken with respect to the test drug and about the patient’s outcome.

6.2.1 Pregnancies

Pregnancies and suspected pregnancies (including a positive pregnancy test regardless of age or disease state) of a female subject occurring while the subject is on lenalidomide, or within 28 days of the subject’s last dose of lenalidomide, are considered immediately reportable events. Lenalidomide is to be discontinued immediately. The pregnancy, suspected pregnancy, or positive pregnancy test must be reported to Celgene Drug Safety immediately by facsimile or email using the Pregnancy Initial Report Form. The female subject should be referred to an obstetrician-gynecologist, preferably one experienced in reproductive toxicity for further evaluation and counseling.

The Investigator will follow the female subject until completion of the pregnancy, and must notify Celgene Drug Safety immediately about the outcome of the pregnancy (either normal or abnormal outcome) using the Pregnancy Follow-up Report Form. If the outcome of the pregnancy was abnormal (e.g., spontaneous or therapeutic abortion), the Investigator should

report the abnormal outcome as an AE. If the abnormal outcome meets any of the serious criteria, it must be reported as an SAE to Celgene Drug Safety immediately by facsimile, or other appropriate method, within 24 hours of the Investigator's knowledge of the event using the SAE Report Form.

All neonatal deaths that occur within 28 days of birth should be reported, without regard to causality, as SAEs. In addition, any infant death after 28 days that the Investigator suspects is related to the in utero exposure to the IP should also be reported to Celgene Drug Safety immediately by facsimile, or other appropriate method, within 24 hours of the Investigator's knowledge of the event using the SAE Report Form.

Male Subjects

If a female partner of a male subject taking investigational product becomes pregnant, the male subject taking lenalidomide should notify the Investigator, and the pregnant female partner should be advised to call their healthcare provider immediately.

6.2.2 Celgene Drug Safety Contact Information:

Celgene Corporation
Global Drug Safety and Risk Management
[name]
[name]
[name]
[contact]
E-mail: [contact]

6.3 Adverse events – RAD001

Information about all adverse events, whether volunteered by the subject, discovered by investigator questioning, or detected through physical examination, laboratory test or other means, will be collected and recorded and followed as appropriate.

An adverse event is the appearance or worsening of any undesirable sign, symptom, or medical condition occurring after starting the study drug even if the event is not considered to be related to study drug. Medical conditions/diseases present before starting study drug are only considered adverse events if they worsen after starting study drug. Abnormal laboratory values or test results constitute adverse events only if they induce clinical signs or symptoms, are considered clinically significant, or require therapy.

The occurrence of adverse events should be sought by non-directive questioning of the patient at each visit during the study. Adverse events also may be detected when they are volunteered by the patient during or between visits or through physical examination, laboratory test, or other assessments. As far as possible, each adverse event should be evaluated to determine:

1. the severity grade (mild, moderate, severe) or (grade 1-4)

-
2. its relationship to the study drug(s) (suspected/not suspected)
 3. its duration (start and end dates or if continuing at final exam)
 4. action taken (no action taken; study drug dosage adjusted/temporarily interrupted; study drug permanently discontinued due to this adverse event; concomitant medication taken; non-drug therapy given; hospitalization/prolonged hospitalization)
 5. whether it constitutes a serious adverse event (SAE)

All adverse events should be treated appropriately. Such treatment may include changes in study drug treatment including possible interruption or discontinuation, starting or stopping concomitant treatments, changes in the frequency or nature of assessments, hospitalization, or any other medically required intervention. Once an adverse event is detected, it should be followed until its resolution, and assessment should be made at each visit (or more frequently, if necessary) of any changes in severity, the suspected relationship to the study drug, the interventions required to treat it, and the outcome.

Information about common side effects already known about the investigational drug can be found in the [\[Investigators' Brochure\]](#). This information should be included in the patient informed consent and should be discussed with the patient during the study as needed.

Serious adverse events

A serious adverse event is an undesirable sign, symptom or medical condition which:

- is fatal or life-threatening
- results in persistent or significant disability/incapacity
- constitutes a congenital anomaly/birth defect
- requires inpatient hospitalization or prolongation of existing hospitalization, unless hospitalization is for:
 - routine treatment or monitoring of the studied indication, not associated with any deterioration in condition (specify what this includes)
 - elective or pre-planned treatment for a pre-existing condition that is unrelated to the indication under study and has not worsened since the start of study drug
 - treatment on an emergency outpatient basis for an event not fulfilling any of the definitions of a SAE given above and not resulting in hospital admission
 - social reasons and respite care in the absence of any deterioration in the patient's general condition
- is medically significant, i.e., defined as an event that jeopardizes the patient or may require medical or surgical intervention to prevent one of the outcomes listed above

To ensure patient safety, every SAE, **regardless of suspected causality**, occurring

- after the patient has provided informed consent and until 4 weeks after the patient has stopped study treatment/participation
- after the patient is randomized and until 4 weeks after the patient has stopped study treatment

-
- after the patient begins taking study drug and until 4 weeks after the patient has stopped study treatment
 - after protocol-specified procedures begin (e.g., placebo run-in, washout period, double-blind treatment, etc.) and until 4 weeks after the patient has stopped study treatment
 - after the start of any period in which the study protocol interferes with the standard medical treatment given to a patient (e.g., treatment withdrawal during washout period, change in treatment to a fixed dose of concomitant medication) and until 4 weeks after the patient has stopped study treatment

must be reported to Novartis within 24 hours of learning of its occurrence. Any SAEs experienced after this 4-week period should only be reported to Novartis if the investigator suspects a causal relationship to the study drug. Recurrent episodes, complications, or progression of the initial SAE must be reported as follow-up to the original episode within 24 hours of the investigator receiving the follow-up information. An SAE occurring at a different time interval or otherwise considered completely unrelated to a previously reported one should be reported separately as a new event.

The investigator must assess and record the relationship of each SAE to each specific study drug (if there is more than one study drug), complete the SAE Report in English, and send the completed, signed form by [contact]) within 24 hours to the Novartis Clinical Safety and Epidemiology Department.

The original copy of the SAE Report and the fax confirmation sheet must be kept within the Trial Master File at the study site.

Follow-up information is sent to the same person to whom the original SAE Report Form was sent, using a new SAE Report Form stating that this is a follow-up to the previously reported SAE and giving the date of the original report. Each re-occurrence, complication, or progression of the original event should be reported as a follow-up to that event regardless of when it occurs. The follow-up information should describe whether the event has resolved or continues, if and how it was treated, whether the blind was broken or not (if applicable), and whether the patient continued or withdrew from study participation.

If the SAE is not previously documented in the [Investigator's Brochure] or Package Insert (new occurrence) and is thought to be related to the Novartis study drug, a Clinical Safety and Epidemiology Department associate may urgently require further information from the investigator for Health Authority reporting. Novartis may need to issue an Investigator Notification (IN), to inform all investigators involved in any study with the same drug that this SAE has been reported. Suspected Unexpected Serious Adverse Reactions (SUSARs) will be collected and reported to the competent authorities and relevant ethics committees in accordance with Directive 2001/20/EC or as per national regulatory requirements in participating countries.

Novartis instructions for rapid notification of serious adverse events

The principal investigator has the obligation to report all serious adverse events to the FDA, IRB, and Novartis Pharmaceuticals Clinical Safety and Epidemiology Department (CS&E).

All events reported to the FDA by the investigator are to be filed utilizing the Form FDA 3500A (MedWatch Form).

All events must be reported, by [contact]), to Novartis Pharmaceuticals CS&E Department within 24 hours of learning of it's occurrence. This includes serious, related, labeled (expected) and serious, related, unlabeled (unexpected) adverse experiences. All deaths during treatment or within 30 days following completion of active protocol therapy must be reported within 5 working days.

Any serious adverse event occurring after the patient has provided informed consent and until 4 weeks after the patient has stopped study participation must be reported. This includes the period in which the study protocol interferes with the standard medical treatment given to a patient (e.g. treatment withdrawal during washout period, change in treatment to a fixed dose of concomitant medication).

Serious adverse events occurring more than 4 weeks after study discontinuation need only be reported if a relationship to the Novartis study drug (or therapy) is suspected.

For Comparator Drugs/Secondary Suspects (Concomitant Medications), all serious adverse experiences will be forwarded to the product manufacturer by the investigator.

Pregnancies

Any pregnancy that occurs during study participation should be reported. To ensure patient safety each pregnancy must also be reported to Novartis within 24 hours of learning of its occurrence. The pregnancy should be followed up to determine outcome, including spontaneous or voluntary termination, details of the birth, and the presence or absence of any birth defects, congenital abnormalities, or maternal and/or newborn complications.

6.3.1 Novartis Drug Safety Contact Information:

CS&E Department
Novartis Pharmaceuticals Corporation
[contact]

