3.3.2 Everolimus

The data described below reflect exposure to AFINITOR (n=274) and placebo (n=137) in a randomized, controlled trial in patients with metastatic renal cell carcinoma who received prior treatment with sunitinib and/or sorafenib. The median age of patients was 61 years (range 27-85), 88% were Caucasian, and 78% were male. The median duration of blinded study treatment was 141 days (range 19-451) for patients receiving AFINITOR and 60 days (range 21-295) for those receiving placebo. The most common adverse reactions (incidence $\geq 30\%$) were stomatitis, infections, asthenia, fatigue, cough, and diarrhea. The most common grade 3/4 adverse reactions (incidence $\geq 3\%$) were infections, dyspnea, fatigue, stomatitis, dehydration, pneumonitis, abdominal pain, and asthenia. The most common laboratory abnormalities (incidence $\geq 50\%$) were anemia, hypercholesterolemia, hypertriglyceridemia, hyperglycemia, lymphopenia, and increased creatinine. The most common grade 3/4 laboratory abnormalities (incidence $\geq 3\%$) were lymphopenia, hyperglycemia, anemia, hypophosphatemia, and hypercholesterolemia. Deaths due to acute respiratory failure (0.7%), infection (0.7%) and acute renal failure (0.4%) were observed on the AFINITOR arm but none on the placebo arm. The rates of treatment-emergent adverse events (irrespective of causality) resulting in permanent discontinuation were 14% and 3% for the AFINITOR and placebo treatment groups, respectively. The most common adverse reactions (irrespective of causality) leading to treatment discontinuation were pneumonitis and dyspnea. Infections, stomatitis, and pneumonitis were the most common reasons for treatment delay or dose reduction. The most common medical interventions required during AFINITOR treatment were for infections, anemia, and stomatitis.

4 Study Objectives and Endpoints

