4.1 Objectives

4.1.1 Primary objectives

- Determine the maximum tolerated dose (MTD) and define the phase II recommended dose (P2RD) for the combination of lenalidomide and everolimus in patients with advanced solid malignancies
- Assess the safety and tolerability of the combination of everolimus and lenalidomide in patients with advanced solid malignancies

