4.2 Endpoints

4.2.1 Primary Endpoint

Maximum tolerated dose (MTD) of the combination of lenalidomide and everolimus

Safety will be assessed according to NCI CTCAE 4.0 (Appendix C)

Assessment of DLT will be performed during the first cycle only and the following will constitute DLT in this study:

- Grade 4 hematologic toxicity lasting more than 7 days
- Grade 4 Neutropenia of any duration with fever $\geq 38.5^{\circ}\text{C}$
- Grade ≥ 3 nausea and or vomiting in spite of standard supportive therapy
- Grade ≥ 3 non-hematologic toxicity (exclude alopecia)
- Inability to re-treat patient within 2 wks of scheduled treatment due to treatment-related toxicity
- Inability to deliver all doses of Everolimus during the first cycle due to an unexpected drug-related toxicity (if everolimus related toxicity is an expected toxicity as per current package insert, then it will not be considered a DLT). These subjects should be discontinued from the study.
- Discontinuation of the study prior to completing the entire first treatment cycle for reasons other than DLT, a subject will be added to that dose-level cohort.
- The occurrence of one of the above drug-related toxicities will result in a clinical and/or laboratory assessment to be performed within 7 days following the initial finding to examine the subject for resolution of the toxicity. Lack of resolution of any of these toxicities according to the guidelines above will be considered a DLT and result in discontinuation of that subject

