10.4 Safety evaluation

Data from all subjects who receive any protocol therapy will be included in the safety analyses. Subjects who entered the study and did not receive any protocol therapy and had this confirmed, will not be evaluated for safety.

The severity of the toxicities will be graded according to the NCI CTCAE v4.0 whenever possible. The safety analysis will be conducted on all enrolled patient population. The following safety parameters will be evaluated:

Adverse Events

A treatment-related adverse event (TRAE) is defined as a sign or symptom that emerges during treatment or within 30 days after the last dose of study drug, having been absent pre-treatment or that has worsened relative to the pretreatment state. Any adverse events deemed related to study drug will also be considered a TRAE regardless of the elapsed time since the last dose of study drug. Adverse events will be coded using the Medical Dictionary for Regulatory Activities (MedDRA) to categorize the event to a system organ class and a preferred term. The number of subjects who experienced at least 1 adverse event, severe (\geq Grade 3) adverse event, study drug-

related adverse event, serious adverse event, and the number of subjects discontinued due to adverse events will be summarized by dose level. For each system organ class and preferred term, summaries will be made with respect to the number and proportion of subjects having at least 1 occurrence of an adverse event during the study. The incidence of adverse events will be presented overall, by system organ class and preferred term, intensity (based on CTCAE Version 4.0), TRAEs, and additional grouping by severity and relationship to study drug. An individual listing of adverse events will be provided. DLTs and study drug-related \geq Grade 2 adverse events will be listed individually.

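### Section 10.4 tabulates adverse events only, so asymptomatic, untreated Grade 3-4 laboratory values (most clearly lymphopenia and anemia) can be under-reported in the safety tables; it also names two safety populations

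*Combined protocol and SAP*

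**What the plan says.** Section 4.1.1 makes safety a primary objective: "Assess the safety and tolerability of the combination of everolimus and lenalidomide in patients with advanced solid malignancies". Section 4.2.1 sets CTCAE 4.0 as the grading standard.

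Section 10.4 introduces its content with "The following safety parameters will be evaluated" and then gives a single heading, Adverse Events. Under it come counts by dose level, system organ class, preferred term, intensity and relationship, plus individual listings of DLTs and of drug-related events of Grade 2 or higher. There is no table of laboratory values by CTCAE grade and no shift table.

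Whether a laboratory finding enters those counts depends on section 6.3: "Abnormal laboratory values or test results constitute adverse events only if they induce clinical signs or symptoms, are considered clinically significant, or require therapy". The rule has no grade threshold. It stands under the everolimus heading, but apart from the TRAE definition in 10.4 there is no other general definition of an adverse event. Section 6.2, on lenalidomide, asks the investigator to appraise every abnormal result, again by judgement of clinical significance.

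On the population, 10.4 first says "Data from all subjects who receive any protocol therapy will be included in the safety analyses", and adds that subjects confirmed as untreated are not evaluated. A few lines later it says "The safety analysis will be conducted on all enrolled patient population".

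**The concern.** A laboratory toxicity rate in a phase I combination study should follow from the graded value. Here it can depend on whether the investigator thought the value mattered. Two patients with the same Grade 3 lymphocyte count at the same dose level can be counted differently, and the difference cannot be seen in the table.

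This matters because the protocol itself expects such findings. In the background on adverse events (subsection 3.3.2, Everolimus) it states that the commonest Grade 3/4 laboratory abnormalities "were lymphopenia, hyperglycemia, anemia, hypophosphatemia, and hypercholesterolemia", and it reports these separately from clinical reactions. A table limited to adverse events cannot be set against that laboratory profile. The double definition of the safety population is a smaller matter, but it leaves the denominator of every safety rate open.

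**Working it through.** The plan states no figure on this point, so there is none to reproduce. The check is mainly of the text.

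**1. Which severe values would still reach the adverse event tables?** Section 6.3 admits a value that needs therapy or is judged significant, so the question is which values the protocol itself acts on.

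| Severe laboratory value | Rule that prompts a hold or treatment | Likely to be recorded under 6.3? |
|---|---|---|
| Neutropenia | Table 5 (Grade 4, or Grade 3 with fever); Table 6 (Grades 3 and 4) | Mostly yes |
| Thrombocytopenia, Grade 3 or higher | Tables 5 and 6 | Mostly yes |
| Hyperglycemia, hypophosphatemia | General Grade 3 non-hematologic rows of Tables 5 and 6 | Mostly yes |
| Hypercholesterolemia | Drug treatment from Grade 2 (section 5.7.7) | Yes |
| Lymphopenia | No row in either table | Only if symptomatic, treated or judged significant |
| Anemia | No row in either table | Only if symptomatic, treated (for example transfused) or judged significant |

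Of the five everolimus Grade 3/4 laboratory abnormalities, three have an action rule and two do not. The conditions for a new cycle in section 5.7.2 do not close the gap. Beyond the neutrophil and platelet limits they refer to drug-related adverse events, so they presuppose that the value was classed as one.

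**2. Does the DLT listing catch the rest?** DLTs are defined by grade in 4.2.1 and do not depend on 6.3, but they cover cycle 1 only. The hematologic criteria require Grade 4 for more than 7 days, or Grade 4 neutropenia with fever. Grade 3 lymphopenia or anemia does not meet them, and nothing after day 28 is assessed. The lenalidomide experience in section 5.2.2 shows that the later period matters: at 25 mg/day the first 28 days were well tolerated, and Grade 3 thrombocytopenia and Grade 3 and 4 neutropenia appeared in the second month.

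**3. Are the data there?** The schedule in section 2 has hematology and chemistry at screening, cycle 1 days 1 and 15, day 1 of later cycles, and discontinuation. A worst grade can be derived from these.

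**4. Illustration of size; every rate is assumed.** With n patients, a true Grade 3-4 rate p and a share s recorded as adverse events, the expected number of affected patients is n × p, and the expected number tabulated is n × p × s.

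- n = 45, p = 3%, 10%, 20%: 1.35, 4.5 and 9 affected. With s = 0.5, the table shows 0.7, 2.3 and 4.5.
- n = 15 (expansion cohort), p = 10%: the chance of at least one tabulated case is 1 − (1 − p × s)^15. For s = 1 it is 1 − 0.90^15 = 79.4%. For s = 0.5 it is 1 − 0.95^15 = 53.7%. For s = 0.25 it is 1 − 0.975^15 = 31.6%.
- Upper bound, if nothing is recorded (s = 0) and p is 3% to 15%: 45 × 0.03 = 1.35 to 45 × 0.15 = 6.75, or about 1 to 7 patients missing per analyte. Step 1 shows that this bound is unrealistic for most analytes.

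**5. Denominator.** Take 9 patients with an event among 45 enrolled, which is 20.0%. If 0, 1, 2 or 4 were never dosed (assumed), the rate among treated patients is 9/45 = 20.0%, 9/44 = 20.5%, 9/43 = 20.9% or 9/41 = 22.0%.

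**The case against.** The best defence is that most severe values will be recorded anyway. Section 6.3 counts interruption or discontinuation of study drug among the ways of treating an event, Tables 5 and 6 call for holds at Grade 3 or 4 for most toxicities, and a value that stops treatment is hard to call unimportant. This largely stands for neutropenia, thrombocytopenia, hyperglycemia, hypophosphatemia and hyperlipidemia. It is still an inference, because 6.3 describes a hold as a response to an event already recognised as adverse. It does not reach lymphopenia or anemia.

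Second, sections 10.1 and 10.3 list all data by subject and summarize continuous variables, so laboratory results are not left out of the report. That is correct. But means, standard deviations and ranges do not say how many patients reached Grade 3 or 4 at a dose level, and a listing leaves that count to the reader.

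Third, the wording "is defined as a sign or symptom that emerges during treatment or within 30 days after the last dose of study drug" defines only the TRAE category. The other counts in 10.4 are not limited to signs or symptoms. This stands, and the point rests on 6.3.

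A reader might go further and infer that the safety result omits the drugs' commonest severe toxicities. The documents do not support that. Subsection 3.3.2 gives clinical reactions and laboratory abnormalities as separate lists without individual rates, so neither can be ranked above the other. Of the nine common severe everolimus reactions in section 5.7.5, four (infections, stomatitis, fatigue, pneumonitis) are clinical, and several of the laboratory ones prompt action. A reader might also infer that a laboratory DLT could be missed and the MTD biased. That does not follow either: 4.2.1 defines DLTs by toxicity and grade, 10.4 lists them individually, and nothing says they are scored from adverse event forms.

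**Conclusion.** The point holds in a limited form. Following the plan as written, an asymptomatic, untreated Grade 3-4 laboratory value judged not clinically significant need not appear in any planned safety table. The exposure is clearest for lymphopenia and anemia, and for values after cycle 1, when the grade-based DLT criteria no longer apply. The affected output serves a primary objective, so it is worth correcting, but the MTD does not depend on it.

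The size cannot be fixed from the documents, because neither the Grade 3-4 rates nor the share that investigators would record is given. The figures above are illustrations, and the range of about 1 to 7 of 45 is an upper bound that assumes none are recorded.

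The two population statements in 10.4 contradict each other. Two sentences point to treated subjects and one to enrolled, which looks like a drafting slip. A reader might infer that it materially dilutes the rates. Under the assumptions tried, the difference is at most about 2 percentage points, and it is zero if every enrolled patient is dosed.

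**What to change.** In section 10.4, add a laboratory heading with a table of worst post-baseline CTCAE v4.0 grade, and the shift from baseline grade, for hematology and chemistry. Present it by dose level, for cycle 1 and overall, and derive it from the laboratory values whether or not an adverse event was recorded. The definition in 6.3 can stay, since the new table does not depend on it. No change to DLT scoring is needed.

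In the same section, delete the sentence that applies the safety analysis to all enrolled patients, so that the safety population is all treated subjects, as the two opening sentences already state.

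The cost is a few lines of text and one or two tables from samples already scheduled, with no extra patients or visits. Laboratory toxicity rates may look slightly less favourable than under adverse event reporting alone.
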